6.1.2 Part B - Cohort Expansion

Once Part A (Dose Escalation) is completed, Part B will enroll a maximum of 150 additional patients with advanced solid tumors with high Globo H expression (defined as an H-score cutoff \geq 100 using a validated IHC assay) across 4 disease specific cohorts and 1 basket cohort based

Page 29

Part B will be conducted to obtain additional safety data, characterize the PK and PD profile of OBI-888, obtain a preliminary assessment of the clinical activity of OBI-888 in Globo H expressing solid tumors, and inform subsequent efficacy-finding clinical development.

No DLTs have been observed at any dose level tested in Part A, and the MTD has not been reached. Therefore, dosing in Part B will be initiated at the highest dose tested in Part A (20 mg/kg OBI-888).

The following 5 cohorts of patients who have high expression of Globo H by a qualified laboratory assessment (ie, Globo H H-score \geq 100 using a validated IHC assay) will be enrolled in Part B.

- Cohort 1: Pancreatic cancer
- Cohort 2: Esophageal cancer
- Cohort 3: Gastric cancer
- Cohort 4: Colorectal cancer
- Cohort 5: Basket (any solid tumor type other than those included in Cohorts 1 through • 4)

All patients are required to provide a tumor biopsy sample, either unstained slides (preferred) or a formalin fixed paraffin embedded (FFPE) tissue block at the initiation of screening visit for screening of Globo H overexpression and confirmation for eligibility of patients for Part B. Patients with a confirmed and documented Globo H H-score of ≥ 100 will be eligible for the study, and will subsequently enter the 28-day screening period to complete the remaining screening procedures.

Patients will continue to receive treatment with OBI-888 until progressive disease, unacceptable toxicity, or decision by the Investigator or patient to discontinue treatment.

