| f. | Post infusion samples at the end of infusion and later (at 1, 3, and 6 hours after the end of the infusion) can be collected in a window of ±15 minutes |
| g. | ADA sample will be collected along with the pre-infusion PK samples according to the above table. For subjects with persistent antibodies at end of study, an |
| | additional ADA sample will be collected at 4 months after the end of study visit. |
| h. | Glycan analysis: Residual PK and ADA samples will be pooled for glycan analysis after PK and ADA data are finalized. |
| i. | Samples should be collected to evaluate tumor-specific biomarkers (eg, CEA for colorectal, gastric, and esophageal cancer; and CA19-9 for pancreatic |
| | cancer). |
| j. | This intensive PK sampling will be collected only from first 3 patients in each cohort. |
| k. | For C1D2 and C1D4, samples can be collected in a window of ±2 hours: |
| | • 24 hours after end of infusion (for infusion at C1D1). |
| | • 72 hours after end of infusion (for infusion at C1D1). |
| 1. | Blood sample will be collected pre-infusion and end-of-infusion. |

- m. For Part B, pre-screening for Globo H tumor sample analysis may occur prior to the screening period for participation in the OBI-888-001 study.
- n. Tumor biopsy samples obtained during the initial screening visit should be used for this assessment.

10 Clinical Activity Profile Assessments

Radiology (CT or MRI scan) evaluations (± 7 days) of tumor response are to be performed during screening within 28 days prior to Cycle 1 Day 1 (first dose of study medication), and thereafter during the study every 8 weeks (Q8wk; ± 1 week) for the first 6 months, then every 12 weeks (Q12wk; ± 1 week). Unscheduled scans can be performed anytime, if needed to confirm disease progression. Radiology assessment for end of study follow-up and early termination should be performed unless the last exam was ≤ 8 weeks prior to permanent discontinuation of study drug. The same assessment method and the same technique should be used on each patient while on study.

Overall tumor response and progression will be evaluated by the Investigator according to RECIST, version 1.1.

11 Pharmacokinetics

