14.4 Pharmacokinetic Analysis

PK parameters will be calculated using a non-compartmental method from the PK samples collected on Dose 1 and will include C_{max} , total exposure (AUC), $t_{1/2}$, Cl, T_{max} , and V_d . To assess the attainment of steady state, trough (C_{min}) concentrations and peak concentrations (end of infusion) of each dose would be obtained directly from analytical data.

Summary statistics will be tabulated for the PK parameters of OBI-888 on Dose 1. Geometric means and coefficients of variation will be presented for C_{max} , AUC, $t_{1/2}$, Cl, and V_d . Median, minimum, and maximum will be presented for T_{max} .

To describe the dependency on dose, scatter plots of C_{max} and AUC versus dose will be provided. Summary statistics will be tabulated for the trough (C_{min}) concentration and peak concentrations (end of infusion) by dose and study day. To assess the attainment of steady state, geometric mean C_{min} values will be plotted versus study day by dose.

Pharmacometric methods may also be applied to further investigate OBI-888 exposure (e.g., accumulation of OBI-888, presence of dose- or time-dependent OBI-888 PK behavior, verification of influential factors on OBI-888 PK).

Based on the PK data (PK profile of first dose, steady-state trough serum concentrations, C_{trough} , or $C_{min,ss}$) and targeted concentration (IC₅₀ in xenograft model), a PK modeling will be carried out for various dose regimens including 15 mg/kg weekly, 15 mg/kg every 2 weeks, or 15 mg/kg q3 weeks. Simulated C_{trough} of desired regimen should be above the targeted serum concentration. The steady-state trough serum concentrations should be above 2.4 ug/mL, from the preclinical xenograft model exhibiting IC₅₀ (trough level at 50% tumor inhibition) of 2.4 ug/mL.

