9. ANALYSIS POPULATIONS

Safety population: all enrolled patients who received at least 1 dose of study drug. This analysis set will be used for all endpoints and analyses except PK.

PK population: all enrolled patients who received at least 1 dose of study drug and had sufficient PK samples (a sample at the end of administration and at least 3 samples during the elimination phase) will be included in the PK assessments. This analysis set will be used for all PK endpoints.

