 - KIR, HLA, Fc receptor gamma genotyping: blood sample will be collected at C1D1 (pre-infusion) and end of study/early termination.

TABLE 14-3 PART B – PHARMACOKINETIC, ADA, AND BIOMARKER SAMPLING SCHEDULE

Cycle (C)	Scree ning	Cycle 1			Cy cle 2	Every 2 cycle s starti ng with Cycle 3 a	Every 2 cycl es starti ng with Cycle 4°	EoS / ET			
Cycle Day	-28 to -1 days	D 1	D2	D4	D 8	D 1 5	D2 2	D1	D1	D1	±7 days
Pharmacokinetic Samples											
Before infusion		X^d			Xb	Xb		Xp		Xb	
End of infusion (90 minutes) ^f		X	X ^{j,k}	X ^k		Х					
1 hour after end of infusion (150 minutes) ^{e,f}		Χ ^j									
3 hours after end of infusion (270 minutes) ^{e,f}		Χ ^j									
6 hours after end of infusion (450 minutes) ^{e,f}		X ^j									
Immunogenicity studies (ADA) ^g		Χ						Х		Х	Χ
Glycan analysish		Χ			Χ	Χ		Х		Χ	Χ
Biomarkers											
Globo H	X										
ADCC/CDC (humoral) ^{d,l}		Χ			Χ	Х					
KIR, HLA, Fc receptor gamma genotyping ^d		Х									
Multiplex IHC ⁿ	Х										
Diagnostic marker ⁿ	X										

Review Status: Final Version: 2.0 Version Date: 02JUN2022

SSEA-3/SSEA-4 ⁿ	Χ						
Surrogate biomarker ^{d,i}		Х				Х	

ADA = antidrug antibody; ADCC = antibody-dependent cell-mediated cytotoxicity; C = cycle; CDC = complement dependent cytotoxicity; D = day; EoS/ET = End of Study/Early

Termination; HLA = human leukocyte antigen; IHC = immunohistochemistry; KIR = killer cell immunoglobulin-like receptor; SSEA = stage-specific embryonic antigens

Note: OBI-888 infusion should be administered on Days 1, 8, 15, and 22 of every 28 day cycle throughout the study treatment period.

The infusion duration of Cycle 1 and Cycle 2 are 90 minutes, and can be reduced to 30-60 minutes from Cycle 3, if there were no infusion related adverse events on prior infusions and at the discretion of the investigator.

- a. Samples to be collected on Day 1 of C3, C5, C7, C9, C11, and C13.
- b. Pre-infusion serum samples can be collected at any time prior to the infusion on the day of the infusion.
- c. Samples to be collected on Day 1 of C4, C6, C8, C10, and C12.
- C1D1 Pre-infusion serum samples can be drawn within 1 day prior-to the infusion.
- e. If there is change of the infusion rate or interruption of infusion, the PK sampling at Day 1 are to be collected from the exact time of completion of infusion to obtain the post-infusion samples at 1, 3, 6 hour at the end of infusion. Exact time of sample collection and the reason for interruption should be documented in the eCRF.

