3.4. Definition and Estimation of Individual NCA PK Parameters

PK parameters will be estimated through a NCA using version 8.2 or later of Phoenix® WinNonlin® (Pharsight Corporation, Cary, NC). Actual post-dose time will be used for the estimation of PK parameters instead of nominal time. Individual PK parameter estimates will be listed (PK Listing 5).

Phoenix® WinNonlin® NCA will use the following settings to compute parameters from plasma PK data:

- Linear Up Log Down calculation method
- Uniform weighting
- Intravenous dose
- Plasma Model Type
- Lambda Z Acceptance Criteria
 - Rsq adjusted ≥ 0.80
 - Span ≥ 2.0 half-lives
 - Includes ≥ 3 timepoints after Tmax

 T_{max} (hour): Time to reach the maximum concentration

- directly taken from the observed concentration

 C_{max} (µg/mL): Maximum concentration

- directly taken from the observed concentration

C_{last} (µg/mL): Concentration at last quantifiable time point

Version: 2.0 Version Date: 02JUN2022

Review Status: Final

- directly taken from the observed concentration

 λ (1/h): Elimination rate constant associated with the terminal phase

- estimated terminal slope of the linear regression of log-transformed concentration vs time
- The regression analysis should contain data from at least 3 different time points in the terminal phase and as many data points as possible, always including the last quantifiable concentration but excluding the concentration at $T_{\rm max}$.
- The coefficient of determination Adj_RSq² should be larger than or equal to 0.80. If at least one of these three conditions is not fulfilled, the terminal half-life and the parameters depending on t½ will be listed but flagged as not reliably calculated. They will generally be excluded from descriptive statistics and statistical testing procedures.

t_{1/2} (h): Terminal elimination half-life

$$- t_{1/2} = \frac{\log_e 2}{\lambda}$$

AUC_{last} (h*µg/mL): Area under the concentration-time curve from time zero to time the last quantifiable time, calculated by log-linear trapezoidal rule.

 $AUC_{\infty}(h*\mu g/mL)$: Area under the concentration-time curve from time zero to infinite time

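### On a Dose 1 reading, the single PK population shuts out every Part B patient after the first 3 in each cohort, including from the peak and trough summaries their samples could support

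*SAP*

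**What the plan says.** SAP section 9 admits to the PK population those treated patients who "had sufficient PK samples (a sample at the end of administration and at least 3 samples during the elimination phase"). It adds: "This analysis set will be used for all PK endpoints". SAP Appendix III, section 3.1, repeats the definition. Neither place names the dose to which the sample count refers.

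The Part B sampling schedule is in Protocol Table 9-3, repeated as SAP Table 14-3. The 1 h, 3 h, 6 h and Day 2 (24 h) samples carry footnote j: "This intensive PK sampling will be collected only from first 3 patients in each cohort". The Day 1 end-of-infusion, Day 4 and pre-infusion Day 8 samples do not carry it, so as printed they apply to everyone. So do the pre-infusion samples at Day 15, Cycle 2 Day 1 and every second cycle from Cycle 4, and the end-of-infusion sample at Day 15.

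Protocol section 14.4 states that "PK parameters will be calculated using a non-compartmental method from the PK samples collected on Dose 1". It also promises trough and peak summaries by dose and study day. PK parameters are a starred secondary endpoint in SAP section 8.2, and Protocol section 6.1.2 gives as one purpose of Part B to "characterize the PK and PD profile of" OBI-888.

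**The concern.** The entry rule suits intensively sampled patients, while most of Part B is sampled sparsely by design. Neither document gives a separate rule for the sparse patients. If one set governs all PK endpoints, the Part B exposure summaries rest on the first 3 patients enrolled in each cohort, and the peak and trough samples scheduled for everyone else do not reach a summary table.

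Those concentrations should be informative. Protocol section 4.3.1 reports a mean steady-state trough of 11.3 µg/mL at 20 mg/kg. Appendix III section 2.4 gives an assay lower limit of 468.75 ng/mL, or 0.46875 µg/mL. The ratio is 11.3 / 0.46875 = 24.1, so a typical trough is well within assay range. Protocol section 14.4 also sets a reference of 2.4 µg/mL for steady-state trough, and a summary across all of Part B would address it far better than one from 3 patients per cohort.

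**Working it through.** **Step 1. The plan's own enrolment figure, which supplies the denominator.** Protocol section 14.1 and SAP section 7 give 9 patients per cohort in stage 1, 21 more in stage 2, continuation on at least 1 response, success on at least 4 of 30, response rates of 5% and 25%, one-sided alpha 0.05 and 90% power.

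P(success) = Σ over x = 1 to 9 of P(Bin(9, p) = x) × P(Bin(21, p) ≥ 4 − x)

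- p = 0.05: 0.0489, within 0.05.
- p = 0.25: 0.902, against the stated 90%.
- Totals: 5 × 9 = 45; 5 × 21 = 105; 45 + 105 = 150.

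The stated sizes reproduce.

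**Step 2. Scheduled Dose 1 samples after the end of infusion in Part B.**

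| Patients | Later samples | Count | At least 3? |
|---|---|---|---|
| First 3 per cohort | 1, 3, 6, 24, 72, 168 h | 6 | yes |
| All others | 72 h, 168 h (pre-dose Day 8) | 2 | no |
| All others, if the absence of footnote j at Day 4 is a slip | 168 h | 1 | no |

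The 72 h entry is footnote k of Table 9-3, "72 hours after end of infusion (for infusion at C1D1"). The Day 8 entry is footnote b, "Pre-infusion serum samples can be collected at any time prior to the infusion on the day of the infusion".

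**Step 3. Why Dose 1 is the natural reading.** Protocol section 14.4 bases the non-compartmental analysis on Dose 1. Appendix III section 2.3 lists times only up to 168 h after the end of the first infusion. PK Table 2 stops at 169.5 h. Its columns at 4.5 h and 7.5 h are 1.5 + 3 and 1.5 + 6, which are Part B's 3 h and 6 h samples after a 90-minute infusion. So the table shell anticipates Part B data, although section 2.3 lists only the Part A times (1, 4 and 8 h).

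**Step 4. Share excluded.** Those who can qualify number at most 5 × 3 = 15. With all cohorts filled through stage 1 and k of them going on to fill stage 2, N = 45 + 21k and the excluded share is (N − 15)/N.

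| k | N | Excluded | Share |
|---|---|---|---|
| 0 | 45 | 30 | 67% |
| 1 | 66 | 51 | 77% |
| 2 | 87 | 72 | 83% |
| 3 | 108 | 93 | 86% |
| 4 | 129 | 114 | 88% |
| 5 | 150 | 135 | 90% |

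For a single cohort of n the share is (n − 3)/n: 27/30 = 90%, 6/9 = 67%, and nil when n is 3 or fewer.

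**Step 5. What the rule costs beyond the sampling design.** Appendix III section 3.4 separately sets a condition for the terminal slope: "Includes ≥ 3 timepoints after Tmax". Patients with two later samples fail it whatever the population definition. Half-life, clearance, AUC to infinity and terminal volume are therefore limited by the sampling itself. The entry rule additionally removes the end-of-infusion, 72 h and trough concentrations, none of which needs a terminal slope to be summarised.

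**The case against.** A reader might infer that up to 90% of Part B is certainly lost from every PK endpoint and that the sparse samples are thrown away. The documents do not support that.

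- **The dose is not named.** If pre-dose samples before later infusions count as elimination-phase samples, a sparse patient has four (72 h, Day 8, Day 15, Cycle 2 Day 1) and qualifies. This stands as a limit on certainty. It does not remove the problem, because the set used for Cmax would then mix full profiles with single end-of-infusion values.
- **The schedule does not reserve all qualifying samples for the first 3.** The end-of-infusion, 72 h and Day 8 samples are for everyone. Only the complete set is restricted, and the others fall one sample short.
- **Terminal-slope parameters are not lost through the population rule**, as Step 5 shows.
- **Later troughs go unsummarised for everyone.** The Appendix III table shells cover Dose 1 times only, so Day 15 and later samples would have no table even in the first 3 patients. That is a separate gap against Protocol section 14.4, and closing it would not help sparse patients while section 9 still excludes them.
- **The data are not discarded outright.** Appendix III section 3.3 plans by-subject concentration listings and individual plots without itself restricting them to the PK population, and Protocol section 14.4 allows pharmacometric work that could use sparse samples.
- **The 90% is a ceiling.** Protocol section 4.3.1 reports 3 Part B patients as of March 2020, and the SAP has since moved to an abbreviated report on safety and exposure.

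It can also be said that up to 15 intensive profiles, with the Part A patients at 20 mg/kg, are enough to describe the PK profile. That is reasonable for non-compartmental parameters. It is not a reason to leave available peak and trough data out of the summaries.

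**Conclusion.** The concern holds in a limited form. On the Dose 1 reading, Part B patients after the first 3 in each cohort cannot enter the only population that SAP section 9 allows for PK endpoints. The share excluded is at most 90% at full enrolment, 67% if all cohorts fill stage 1 and stop, and zero in any cohort of 3 or fewer. The realised share is unknown because the documents do not give final Part B enrolment.

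The conclusion rests on two assumptions: that the sample count refers to the Dose 1 profile, and that the footnotes are as printed. A missing footnote j at Day 4 would leave these patients further short. The avoidable loss is confined to concentration summaries for a descriptive secondary endpoint. This should be corrected, but it does not affect the safety analysis.

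**What to change.** In SAP section 9 and Appendix III section 3.1, define two sets:

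1. A PK concentration set: treated patients with at least one valid post-dose OBI-888 concentration. Use it for concentration, end-of-infusion and trough summaries.
2. An NCA set: the present rule, stated as applying to the Dose 1 profile. Use it for Cmax, Tmax, AUC, half-life, clearance and volume.

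Report the end-of-infusion concentration in all patients as a measure of its own, and do not pool it with Cmax from intensive profiles. Protocol section 4.3.1 says Cmax was reached by the end of infusion in most patients, not all, so a lone end-of-infusion value could bias pooled Cmax downward.

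Add the Part B sampling times to Appendix III section 2.3, add the peak and trough summary promised in Protocol section 14.4, and show both Ns by cohort.

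The cost is one extra population flag, one or two extra tables, and two denominators for readers of the PK report to keep apart. No new samples are needed.

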10. ANALYTICAL PLAN AND STATISTICAL METHODS

10.1 GENERAL CONVENTIONS AND STATISTICAL CONSIDERATIONS

All statistical analyses will be conducted and data appendices will be created using the SAS system version 9.4 or higher.

Data collected in this study will be presented in patient data listings and summary tables.

Descriptive statistics (number of patients with non-missing values, mean, standard deviation, median, minimum, and maximum) will be presented for continuous variables. All raw data will be presented to the original number of decimal places. Means and medians will be presented to 1 more decimal place than in the raw data. Standard deviations will be presented to 2 more decimal places than in the raw data.

Frequency distributions (counts and percentages) will be presented for categorical variables. Discrete variables that are ordinal-scaled (e.g., ECOG performance score) will additionally be presented with mean scores and standard deviations. If not specified otherwise, the number of observations with non-missing values will be the denominator for percentage calculation. Further details on the handling of missing observations are presented in section 10.3.

If days are converted to months, a factor of 30.4 days/month will be used. If days are converted to years, a factor of 365.25 days/year will be used. Time will be shown in study weeks, i.e. number of weeks from the first administration of any study drug.

Dose escalation (Part A). The dose-escalation analysis will be presented by OBI-888 dose (5 mg/kg, 10 mg/kg or 20 mg/kg) cohorts and overall. The following cohorts and overall will be presented:

- OBI-888 5 mg/kg
- OBI-888 10 mg/kg
- OBI-888 20 mg/kg
- Dose Escalation Total

Expansion cohorts (Part B). The expansion part analysis will be presented by cancer diagnosis. The following cohorts and overall will be presented:

- Cohort 1: Pancreatic cancer
- Cohort 2: Esophageal cancer
- Cohort 3: Gastric cancer
- Cohort 4: Colorectal cancer
- Cohort 5: Basket (any solid tumor type other than those included in Cohorts 1 through 4)

Review Status: Final Version: 2.0 Version Date: 02JUN2022

Cohort Expansion Total

10.2 DEFINITION OF BASELINE, STUDY VISITS, AND VISIT WINDOWS

Baseline for each assessment is defined as the result of the last assessment prior to first dose of study drug. Per protocol, assessments performed at Day 1 should be obtained prior to infusion of the study drug. As only dates (without time) of assessments are recorded, the last assessment with a date prior to or the same as the first dose date will be considered baseline.

The data will be analyzed according to the visits recorded in the eCRF. No additional visit windows will be applied. In listings, any unscheduled visits will be inserted in the appropriate temporal sequence using visit date and time.

10.3 HANDLING OF MISSING DATA

For the calculation of the time since initial cancer diagnosis, the following imputation rules will be applied when the date of initial cancer diagnosis is incomplete:

- If the day is missing: first day of the month.
- If the day and month are missing: first day of January.

Partial or missing start and end dates of AEs and concomitant medications will be imputed conservatively based on the rule described in Appendix II: Imputation rules for missing dates. The imputed dates will be used to allocate the AEs and concomitant medications to a study period, and to determine whether an AE is/is not treatment emergent. Listings of the AEs and concomitant medications will present the actual partial dates; imputed dates will not be shown.

For CBR endpoint, patients with missing data (for any reason) will be included as non-responder.

10.4 PATIENT DISPOSITION

Patients in each analysis population, as well as patients who complete the treatment, complete the study, and patients who prematurely discontinue from treatment and from the study, together the with number of enrolled patients will be tabulated as indicated in section 10.1. The number and percentage within each category will be presented.

The number and percentage of patients included in the safety and PK populations will also be summarized by study part, and cohort (and for Phase B).

A listing with all enrolled patients will be generated for the study to describe country/study center, patient number, study part, cohort, first and last study drug dosing dates, total duration of study drug dosing, the reason for discontinuing study drug dosing, end of study date, and reason for discontinuing the study.

